9. STUDY PROCEDURES

9.1. Subject Screening and Informed Consent

The investigator will obtain written informed consent from each subject as a condition of enrollment in the study. Informed consent will be obtained after providing the prospective study participant with an adequate explanation of the protocol procedures and prior to the subject's participation in the study (including screening procedures).

The content of the informed consent form (ICF) will conform to FDA regulations as defined in 21 CFR Part 50, other necessary Regulations, and must have current Institutional Review Board (IRB)/ Ethics Committee (EC) approval.

The subject will sign the ICF before any study procedures are initiated. The subject or guardian will sign and date one or two copies of the ICF in the presence of the investigator or designee, in accordance with applicable local requirements. A signed original copy will be retained with the subject records, and either a copy of the signed original or another signed original of the ICF will be given to the subject, in accordance with applicable local requirements. .

9.2. Assignment of Subject Identification Number

Once a subject has provided written informed consent, and it has been determined that the subject will undergo screening, a Subject Identification (PtID) Number will be assigned by the study site. The first 2 digits of the PtID number will be the assigned site number as followed by a 3-digit number in sequential order (i.e., 01-001, 01-002, etc.).

The PtID number and subject initials (where permitted by local authorities) are to be recorded on all study documents and will link the documents to the subject's medical record. To maintain confidentiality, the subject's name should not be recorded on any study document other than the ICF.

Only those patients who have been randomized will have Exclusion/Inclusion data recorded on the electronic case report forms (eCRF).

9.3. Randomization

Following confirmation of eligibility at Day 1, subjects will be randomly assigned in a 2:1 ratio to either the FAI insert or sham injection through a central Interactive Voice Response System (IVRS). Randomization will be stratified on the basis of whether the patient is receiving systemic treatment to control uveitis at the time of study entry.

The randomization schedule will be prepared using a blocked randomization and will be generated by an independent statistician.

The treatment assignment will be revealed to the assessing investigator only in emergency situations when medical/supportive care cannot be provided without determining if the subject received the FAI insert.

9.3.1. Unmasking

Unmasking a subject's treatment to the assessing investigator should only be done in emergency situations for reasons of subject safety.

At the initiation of the study, the clinical sites will receive instructions for unmasking a subject.

In the event that an emergency unmasking is required, the assessing investigator/medically qualified designee has the authority to unmask a subject's treatment using IVRS, or its back-up system if IVRS is not functioning. , If possible, the assessing investigator/medically qualified designee should contact the PPD Medical Monitor or designee before breaking the mask.

When the masked treatment code is broken, the date and time of unmasking, name of person doing the unmasking, and the reason for unmasking must be fully documented in the source documentation.

9.4. Screen Failures

Study centers will document all screen failures on the Subject Screening/Enrollment Log with the reason for the failure to be enrolled. Subjects who fail to meet inclusion/exclusion criteria during the screening period or on study Day 1 may be rescreened.

9.5. Study Schedule

See [Table 4](#) for the schedule of visits and assessments. The screening visit and Day 1 (administration of study treatment) are to be within a 30-day period. The windows for the follow-up visits are Day 7: +/- 2 days; Day 28: +/- 3 days; Months 2, 3: +/- 7 days; Months 6, 9, 12, 18, 24, 30 & 36: +/- 28 days.

9.6. Screening

All study data will be collected for the study and fellow eye.

After obtaining informed consent, the following assessments will be performed:

- Demographic information, medical history and ophthalmic history including a detailed history of the subject's posterior uveitis and its management over the previous 12 months
- Physical exam including height, weight and vital signs (includes systolic/diastolic blood pressure and pulse rate after subject is in the sitting position for at least 5 minutes)
- Obtain blood samples for routine clinical laboratory tests (hematology, ESR, serum chemistry)

- HIV and syphilis serology testing
- TB testing
- Ophthalmic exam (including BCVA, IOP [recorded as the mean of three measurements], dilated indirect ophthalmoscopy and anterior, posterior and intermediate slit lamp examinations)
- Visual field
- Collect urine for Urinalysis and for Urine pregnancy test (females of childbearing potential)
- Subjective Ocular Tolerability and Discomfort Assessment
- Concomitant medications
- Verification that the subject satisfies all inclusion and exclusion criteria. Do not continue screening any subject who does not meet the screening eligibility requirements.

9.7. Procedures on Day of Treatment

9.7.1. Designation of Study Eye and Randomization

For subjects with unilateral uveitis, the study eye will be the affected eye. For subjects with bilateral uveitis, the study eye will be the worse eye meeting the inclusion/exclusion criteria. For subjects with symmetrical uveitis the study eye will be the right eye. The non-study eye may receive any local ocular treatment at the discretion of the investigator.

If the subject meets the inclusion and exclusion criteria at Screening and Day 1, the randomization to the FAI insert or sham injection will be performed via the IVRS.

Randomization will be stratified on the basis of whether the patient is receiving systemic treatment to control uveitis at the time of study entry. For patients receiving systemic treatment at time of study entry, randomization will be stratified on the basis of the type of treatment (steroid or immunosuppressant).

To preserve study masking as much as possible within the imposed ethical constraints, the study personnel who administer the assigned treatment will refrain from performing any subject assessments after study Day 1. Treatment assignments will be masked to the subjects and to those involved in administering routine follow-up care to the subjects. Follow-up assessments will only be performed by study personnel at the site who are masked to the assigned treatment.

9.7.2. Data Collection Prior to Injection of FAI Insert or Sham Injection

- Vital signs (blood pressure and pulse rate after subject is in the sitting position for at least 5 minutes)
- Ophthalmic exam (including BCVA, IOP [recorded as the mean of three measurements], dilated indirect ophthalmoscopy and slit lamp examinations)
- Determination of < 10 anterior chamber cells/HPF and a vitreous haze \leq grade 2 for study eye

- OCT
- Urine Pregnancy test
- Concomitant medications
- Subjective tolerability and discomfort assessment
- Verification that the subject satisfies all other inclusion and exclusion criteria

9.7.4. Sham Injection Procedure

Subjects assigned to the sham injection control group will be prepared for injection in the same manner as the subjects in the FAI insert treatment group (steps 1-4 above) and will receive the same post-treatment evaluations and medications as the FAI insert group (steps 6-11 above). Only step 5 is different. When the investigator opens the treatment packaging for a subject assigned to the sham injection control group, the package will contain a syringe with a blunt needle attached. The sham injection will consist of pressing the blunt needle against the sclera of the eye with approximately the same pressure as would be used during the injection of a FAI insert.

9.8. Criteria for FAI Insert Removal

Investigators should consider removing the FAI insert if any of the following events occur:

- Apparent intolerance to insert
- Endophthalmitis
- Partial extrusion or exposure of insert

Based on prior human experience with Iluvien, a product virtually identical to the FAI insert (refer to the Investigator's Brochure for more details), the likelihood that insert removal will become necessary is very small.

9.9. Post-Treatment Visits and Long Term Follow-up

Investigator 2 (masked investigator) will be responsible for all safety and efficacy procedures and assessments following Day 1.

The subject will return to the study site on Day 7, 28 and Months 2, 3, 6, 9, 12, 18, 24, 30, and 36, for a total duration of 36 months. Subjects may be seen more frequently if medically indicated. [Table 4](#) provides descriptions of the ophthalmic assessment procedures to be performed, as indicated, at the scheduled visits. All assessments are made for both eyes of all subjects.

9.9.1. Post-Treatment Follow-up (Days 7 & 28)

Assessments include: Vital signs (blood pressure and pulse rate after subject is in the sitting position for at least 5 minutes); Ophthalmic exam (BCVA, IOP, dilated indirect ophthalmoscopy and anterior, posterior and intermediate slit lamp examinations); OCT (Day 28); subjective ocular tolerability and discomfort assessment; concomitant meds and AEs.

9.9.2. Long-Term Follow-up (Months 2, 3, 6, 9, 12, 18, 24, 30, & 36)

Assessments include: Vital signs (blood pressure and pulse rate after subject is in the sitting position for at least 5 minutes); Ophthalmic exam (BCVA, IOP, dilated indirect ophthalmoscopy and anterior, posterior and intermediate slit lamp examinations); subjective ocular tolerability and discomfort assessment; visual field (Months 12, 24 and 36); OCT, pregnancy test (Months 12, 24 and 36) and concomitant Meds and AEs.

9.10. Concomitant Medications/Procedures

9.10.1. Tapering/Ending Systemic or Topical Uveitis Treatment Following Day1

Subjects may be treated prior to entry in order to meet study inclusion criteria. The objective of prior treatment is to obtain a relatively quiet eye prior to enrollment. If a subject is receiving systemic corticosteroids or immunosuppressants, or topical steroids to control uveitis prior to study enrollment, that subject will have such treatment ended within three months following Day 1, in a manner that follows the standard of care for ending the specific treatment. For example, some systemic treatment regimens may be ended immediately, while others require a period of gradual dose reduction (tapering). Systemic medications or topical steroids administered as part of gradual dose reduction are not considered prohibited medications.

9.10.2. Prohibited Medications

Other than the exceptions described in [Section 9.10.1](#), [Section 9.12](#) or in this section below, the following concomitant medications are not permitted during the study:

- Oral, systemic, injectable, or topical steroids
- Systemic immunosuppressants

Systemic medications or topical steroids administered as part of gradual dose reduction (tapering), as described in [Section 9.10.1](#), are not considered prohibited medications.

Additionally, topical steroids administered as short term standard treatment following an ocular surgical procedure are not considered prohibited medications.

It is advisable for the PI to discuss treatment with the Medical Monitor before administering any prohibited medication unless it is an emergency.

9.10.3. IOP Reduction Therapy

Pharmacologic treatment (eyedrops) of elevated IOP must be instituted whenever the IOP is >30 mmHg, and may be instituted at lower IOP levels, at the discretion of investigator 2 and in accordance with the investigator's standard of care. Treatment may include referral to another ophthalmologist. If IOP does not adequately respond to pharmacologic treatment, alternative treatment should be considered (laser, trabeculectomy). The investigator should obtain information on the treatment administered by non-study ophthalmologists for inclusion in the study records.

9.10.4. Cataract Removal and Other Elective Ocular Surgery

Cataracts are recommended to be removed by extra-capsular extraction with phacoemulsification. A cataract may be removed prior to a subject's enrollment.

Because of the importance of VA evaluations in this study, the timing of cataract removal or any elective surgery during the post-treatment follow-up period should be scheduled at least 4 weeks prior to any study visit involving VA assessment.

9.11. Unscheduled Follow-up Visits

Additional examinations may be conducted as necessary to ensure the safety and well-being of subjects during the study period. Electronic case report forms (eCRFs) should be completed for each unscheduled visit or test that the subject completes.

9.12. Treatment of Recurrences of Uveitis

In the event of a uveitis recurrence in either eye (defined as an “Endpoint”), peri-ocular or intraocular corticosteroid injections, or topical medications should be administered as first line local therapy, in accordance with the protocol. Investigators should consider treatment with topical steroids as first line therapy for a recurrence that involves only an increase in anterior chamber cells with no increase in vitreous opacity. Systemic immunosuppressants or systemic steroids should be used only if local therapy fails.

Subjects who experience a recurrence of uveitis will continue participation in the study. Once the subject’s recurrence is controlled, the treatment regimen (local or systemic therapy) will be ended in a manner that follows the standard of care for ending the specific treatment regimen.

Details of each recurrence and its treatment will be documented in the eCRF.

9.13. Description of Procedures

Refer to [Table 4](#) and the appendices ([Sections 18, 19, and 20](#)) for more details.

9.13.1. Slit Lamp Examination

Slit lamp examination should be performed using the investigator’s standard procedure. This procedure should be the same for all subjects examined at the site and use the same equipment. Observations should be made to indicate the absence or presence of findings for conjunctiva, cornea, iris, and anterior and posterior chambers. All findings are to be documented in the source documentation and the appropriate eCRF.

9.13.2. Dilated Indirect Ophthalmoscopy

Dilated indirect ophthalmoscopy should be performed as part of each ophthalmic examination. This procedure should be the same for all subjects examined at the site and use the same equipment. All findings are to be documented in the source documentation and the appropriate eCRF.

9.13.3. Visual Acuity

BCVA will be measured according to the standard procedure developed for ETDRS at 4 meters or 3 meters if the electronic (E)-ETDRS system is employed. Corrected-distance VA is to be reported as number of letters read correctly by the subject. The details of refraction and VA determination procedures are provided in [Section 18](#).

9.13.4. OCT

Optical coherence tomography (OCT) will be performed; Cirrus or Spectralis instruments are preferred.

9.13.5. Intraocular Pressure

Applanation tonometry (preferably Goldmann) will be used for IOP measurements where an average of 3 measurements will be recorded using the investigator's standard procedure.

9.13.6. Subjective Ocular Tolerability and Discomfort Assessment

Refer to Appendix 3 ([Section 20](#)) for details:

- Subjective ocular discomfort grading
- Subjective tolerability using visual analog scale for pain

9.14. Laboratory Testing

Clinical laboratory testing will include:

- Hematology (standard tests)
- ESR
- electrolytes: sodium; potassium; chloride; calcium; bicarbonate/CO₂
- renal function: serum creatinine, BUN
- hepatic function: serum bilirubin, alkaline phosphatase, SGOT/AST, SGPT/ALT, total albumin, total protein
- HIV and syphilis serology testing
- Screening test for latent mycobacterium tuberculosis (TB) infection
- Urinalysis (standard tests)
- Urine pregnancy test (for females of childbearing potential)

9.15. Protocol Deviations

The investigator will not deviate from the requirements from this protocol without prior approval from pSivida Corp. unless necessitated by a medical emergency (i.e., those that impact subject safety or the validity of the study). All other significant changes to the protocol will be made by pSivida Corp. as a protocol amendment and approved by IRB/EC and the appropriate regulatory authority prior to implementation.

9.16. Study Termination or Suspension

If the trial is prematurely terminated or suspended for any reason, the investigator/institution should promptly inform the trial subjects, should assure appropriate therapy and follow-up for the subjects, and, where required by the applicable regulatory requirement(s), should inform the regulatory authority.

In addition, if the investigator terminates or suspends a trial without prior agreement of pSivida, the investigator should inform the institution where applicable, and the investigator/institution should promptly inform pSivida and the IRB/IEC, and should provide pSivida and the IRB/IEC a detailed written explanation of the termination or suspension.

If pSivida terminates or suspends this trial, the investigator should promptly inform the institution where applicable and the investigator/institution should promptly inform the IRB/IEC and provide the IRB/IEC a detailed written explanation of the termination or suspension.

If the IRB/IEC terminates or suspends its approval/favorable opinion of this trial, the investigator should inform the institution where applicable and the investigator/institution should promptly notify pSivida and provide pSivida with a detailed written explanation of the termination or suspension.

9.17. Subject Withdrawal Criteria

Subjects have the right to withdraw from the study at any time, for any reason, without jeopardizing their medical care. The following are examples of criteria for considering withdrawal from this study:

- Withdrawal of subject consent; or
- Intercurrent illness including death that prevents continuation of regular follow-up visits

All subjects will be followed for safety through their final visit unless withdrawn from the study for the above reasons.

The investigator, IRB/EC and pSivida Corp. also have the right to withdraw subjects from the study for the following reasons: when continuation may jeopardize the health of the subject, protocol violations, AEs or concurrent conditions, administrative or other reasons.

Subjects who withdraw for any reason from the study following randomization and administration of study treatment (FAI insert or sham injection) will not be replaced. All randomized subjects will be followed for as long as they agree to return for visits.

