7.6. Study Duration

All subjects will be followed for 36 months after treatment.

Figure 2: Study Design

[figure not shown]

Table 4: Schedule of Procedures and Assessments

Assessments	Screening	Day 1	Day 7	Day 28	Months 2, 3	Months 6, 9, 12, 18, 24, 30, 36
Timing/Interval	-30 to 0	1	±2D	±3D	±7D	±28D
Medical/Ophthalmic History	X					
Demographics	X					
Inclusion/Exclusion Criteria	X	X				
Randomization		X				
Pregnancy Test ^a	X	X				X ^a
Vital Signs ^b	X	X	X	X	X	X
Clinical Labs ^c	X					
Ophthalmic Examination ^d	X	X	X	X	X	X
Visual Field ^e	X					X ^e
OCT		X		X	X	X
Physical Exam	X					
Subjective Ocular Tolerability & Discomfort Assessment	X	X	X	X	X	X
FAI Insert Placement or Sham Injection		X				
Concomitant Meds	X	X	X	X	X	X
AEs		X	X	X	X	X

^a Females of child-bearing potential only: urine test conducted only at Screening, Day 1, Month 12, Month 24 and Month 36.

^b Includes systolic/diastolic blood pressure and pulse rate after subject is in the sitting position for at least 5 minutes. Height and weight at Screening only.

^c Hematology; ESR; serum chemistry; urinalysis; HIV and syphilis serology testing; TB testing.

^d Ophthalmic examination includes BCVA, IOP [recorded as the mean of three measurements], dilated indirect ophthalmoscopy, and anterior, posterior and intermediate slit lamp examinations

^e Conducted only at Months 12, 24 and 36.

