14. DATA ANALYSES

14.1. Sample Size

A two group continuity corrected Chi-square test with a 0.05 two-sided significance level will have 89% power to detect the difference between a Sham group recurrence free rate of 0.600 and a FAI treated group recurrence free rate of 0.880 (odds ratio of 0.205) when the sample sizes are 40 and 80, respectively (a total sample size of 120).

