5.1. Disposition

Subject disposition will be summarized for the ITT population. A disposition of subjects includes the number and percentage of subjects for the following categories: subjects randomized, subjects who completed the study, subjects who discontinued from the study, subjects in the Safety population, subjects in the ITT population, and subjects in the Month 6, Month 12 and Month 36 PP populations. All percentages will be based on the number of subjects randomized.

The reasons for study discontinuation will also be summarized in the disposition table. The reason for study discontinuation includes the following: adverse event, lack of efficacy, lost to follow-up, death, subject voluntarily withdrew, physician decision, sponsor decision, and study cancelled.

Subject disposition data will be presented in a listing.

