8.1.2. Data Imputation

Data for the primary outcome only (recurrence of uveitis) will be imputed using a straightforward method:

- A subject who has not previously experienced a recurrence and does not have the required eye examination data for assessing recurrence at Month 6 (or Month 12 or Month 36 for the Month 12 or 36 analyses, respectively) for any reason will be considered as having a recurrence. If one or more of the required eye examinations, including BCVA and vitreous haze, is not completed at Month 6 (or Month 12 or Month 36), the subject will be considered as having a recurrence. Reasons for missing recurrence data at Month 6 (or 12 or 36) include, but are not limited to: discontinuation from the study prior to visit, visit occurred outside of the visit window, and missed visit.
- A subject who has not previously experienced a recurrence and takes a prohibited systemic concomitant medication as defined in Section 9.10.2 of the protocol any time during the study prior to Month 6 (or Month 12 or Month 36 for the Month 12 or 36 analyses, respectively) will be considered as having a recurrence.
- A subject who has not previously experienced a recurrence and takes a prohibited local concomitant medication in the study eye as defined in Section 9.10.2 of the protocol any time during the study prior to Month 6 (or Month 12 or Month 36 for the Month 12 or 36 analyses, respectively) will be considered as having a recurrence.

Systemic medications administered as part of a gradual dose reduction (tapering) (as described in Section 9.10.1 of the protocol) will not be considered prohibited medications for the analysis of the primary endpoint. For the analysis of the primary endpoint for US/FDA, topical steroids will not be considered a prohibited medication.

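### Protocol 9.17 both promises follow-up for as long as the subject agrees and allows others to end it for non-safety reasons; a recurrence-free subject withdrawn that way before the Month 6 examinations is scored as a primary failure

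*Protocol*

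**What the plan says.** Protocol 9.17 contains three statements that bear on follow-up.

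- It names withdrawal of consent and intercurrent illness, including death, as example grounds. It then says that subjects remain in safety follow-up to their final visit unless they left on those grounds.
- It then gives the investigator, the IRB/EC and the sponsor a right to withdraw subjects "when continuation may jeopardize the health of the subject, protocol violations, AEs or concurrent conditions, administrative or other reasons".
- It ends: "All randomized subjects will be followed for as long as they agree to return for visits". Treated subjects who leave are not replaced.

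Other sections support the last statement. Protocol 7.6 says "All subjects will be followed for 36 months after treatment", and protocol 9.12 says "Subjects who experience a recurrence of uveitis will continue participation in the study". SAP 4.2 keeps a subject in follow-up for safety and recurrence to Month 36 even after removal of the insert.

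On the outcome, protocol 14.3.4.2 imputes a recurrence for a subject with no earlier recurrence who lacks the Month 6 eye examinations, whatever the cause. SAP 8.1.2 repeats the rule and lists "discontinuation from the study prior to visit" among the causes. SAP section 4 sets the Month 6 window at Day 152 to Day 208.

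**The concern.** The insert or sham is given once, on Day 1. Withdrawing a subject for a protocol violation or an administrative reason therefore changes no study treatment. All it can do is end the visits at which recurrence is assessed.

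If the visits end before Month 6 and the subject has had no recurrence, the primary endpoint records a failure that nobody observed. The decision rests with people other than the subject, on grounds as open as other reasons, and the same section says that such a subject should still be followed. Sites could read it either way, and the difference would go straight into the primary endpoint.

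**Working it through.** **1. Which withdrawals reach the primary endpoint**

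| Time of withdrawal by others | Recurrence already observed | No recurrence so far |
|---|---|---|
| Before the Month 6 examinations | Failure as observed; no change | Imputed failure in the primary analysis |
| After the Month 6 examinations | Failure as observed; no change | Month 6 result stands; imputed only at Months 12 and 36 |

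The right to withdraw runs for 36 months, but only the upper right cell affects the primary test.

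**2. The plan's own power figure**

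Protocol 14.1 states: "A two group continuity corrected Chi-square test with a 0.05 two-sided significance level will have 89% power". The assumed rates are "a Sham group recurrence free rate of 0.600 and a FAI treated group recurrence free rate of 0.880", with 40 sham and 80 FAI subjects. No dropout allowance is stated there.

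Normal approximation with continuity correction: z = (|p1 − p2| − ½(1/n1 + 1/n2) − 1.96·SE0) / SE1.

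- Corrected difference: 0.28 − ½(1/40 + 1/80) = 0.28 − 0.01875 = 0.26125
- Pooled rate: (24 + 70.4)/120 = 0.7867
- SE0 = √[0.7867 × 0.2133 × (1/40 + 1/80)] = 0.0793
- SE1 = √[0.6 × 0.4/40 + 0.88 × 0.12/80] = 0.0856
- z = (0.26125 − 1.96 × 0.0793)/0.0856 = 1.236, so power is 89.2%

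This reproduces the stated 89%. The odds ratio also reproduces: (0.6/0.4)/(0.88/0.12) = 0.2045. Enumerating the corrected test over both binomial distributions gives an exact power of 90.4%, which is the baseline below.

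**3. Effect of withdrawal before Month 6**

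Let w be the share of otherwise recurrence-free subjects withdrawn by others before the Month 6 examinations. Each becomes an imputed failure, so the recurrence-free rate p becomes p(1 − w). The documents give no value of w; the values here are assumptions.

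| w, both arms | Sham rate | FAI rate | Expected extra failures | Exact power |
|---|---|---|---|---|
| 0 | 0.600 | 0.880 | 0 | 90.4% |
| 2% | 0.588 | 0.862 | 0.02 × (24 + 70.4) = 1.9 | 87.6% |
| 5% | 0.570 | 0.836 | 0.05 × (24 + 70.4) = 4.7 | 83.0% |

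**4. Unequal withdrawal, to show direction only**

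- 5% in FAI and none in sham (0.600 against 0.836): power 73.9%.
- 5% in FAI and 2% in sham (0.588 against 0.836): power 77.8%.
- No true difference, both rates 0.75, and 10% withdrawn in sham only (0.675 against 0.75): the chance of a significant result favouring FAI is 10.1%, against 1.6% with no withdrawal.

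Unequal withdrawal can therefore cost more power or bias the comparison, in either direction.

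**The case against.** The strongest reply is that a reserved right to withdraw is permissive and can sit beside an intention to follow everyone; the plan need not use it. The plan also examines missing outcomes from several sides. SAP 8.1.3 has an analysis that treats missing as no recurrence, a tipping-point analysis and multiple imputation, and the per-protocol population drops imputed endpoints. SAP 4.2.1 keeps the sponsor masked until the Month 6 lock, which limits arm-selective withdrawal by the sponsor. All of this stands. But these analyses only vary the imputed value. They do not recover the outcome, they do not separate withdrawal by others from other missing data, and the primary test still uses the imputed failure.

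A reader might also infer more than the documents support:

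- **That the ITT analysis is defeated.** It is not. Protocol 14.2.1 and SAP 4.3.1 keep every randomized subject in the population as randomized. The observed outcome is lost, not the subject's place in the denominator.
- **That safety follow-up is removed.** The safety sentence in 9.17 excepts only consent and intercurrent illness or death, which come before it. Read literally, subjects withdrawn by others stay in safety follow-up. What final visit means for them is unclear, so this belongs to the same ambiguity.
- **That SAP 5.1 contradicts protocol 9.12.** SAP 5.1 lists "adverse event, lack of efficacy, lost to follow-up, death, subject voluntarily withdrew, physician decision, sponsor decision, and study cancelled". It is a reporting list, not a withdrawal rule. A subject may choose to leave for lack of efficacy, and the category should record that.
- **That the added failures would fall mainly on FAI.** Protocol 9.10.3 and 9.10.4 manage raised pressure and cataract within the study. The pressure and cataract rates cited in the introduction come from follow-up of three to four years. No document gives withdrawal rates by arm before Month 6.

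**Conclusion.** The concern holds in a limited form. Protocol 9.17 gives two incompatible answers on whether a subject withdrawn by others for a non-safety reason is still examined. Under the imputation rule, that gap can decide a primary outcome for a subject who has had no recurrence and is withdrawn before the Month 6 examinations.

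The size depends on a rate that the documents do not give. With equal withdrawal in both arms, the loss of exact power is 2.8 percentage points at 2% (90.4 − 87.6) and 7.4 points at 5% (90.4 − 83.0). These are illustrations and would apply to any loss of Month 6 examinations at those rates; they do not forecast how often the clause would be used. The unequal scenarios show what could happen, and no particular imbalance is claimed. The change is worth making because it is cheap and replaces assumed failures with observed results.

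**What to change.** **Protocol 9.17.** Reconcile the withdrawal right with the section's last sentence. State that a subject withdrawn by the investigator, the IRB/EC or the sponsor on non-safety grounds (protocol violation, administrative or other) remains in follow-up. The subject is asked to attend the scheduled eye examinations, at least at Months 6, 12 and 36, unless the subject withdraws consent.

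**Protocol 14.3.4.2 and SAP 8.1.2.** State that outcomes observed at those examinations are used in the ITT analysis in place of an imputed recurrence, even if the subject is recorded as discontinued.

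**SAP 5.1.** Leave the reporting categories as they are.

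The safety and adverse-event grounds are outside this point. No rule is proposed for them; the sponsor needs to reconcile those parts of 9.17 with its follow-up sentences.

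The cost is a wording amendment and a few visits, already in the schedule, for subjects who would otherwise have left.
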